We believe that the process of undergoing a fertility preservation consultation and/or undergoing an oocyte harvest in itself has a potential therapeutic benefit. Focusing on, “after” a patient’s cancer diagnosis has been suggested to have a positive effect on a

patient's psychosocial state. We wish to explore this theory with implementation of a follow-up interview and the validated Ferti-Qol questionnaire to assess a patient's quality of life. (Boivin et al, 2011) We also plan to assess egg quality in all of our patients to determine the impact of patient demographics and various chemotherapeutics.

Purpose & Objective

Purpose: This investigational study will permit patients to cryopreserve their oocytes, after first obtaining full written informed consent, for the purpose of potential future use under the oversight of the institutional review board, as specified by ASRM and ACOG current guidelines. The data obtained will also contribute to the knowledge base surrounding quality of life issues and fertility preservation in general, and oocyte cryopreservation in particular.

Objective: To determine the long term benefits, in particular impact on patient quality of life and clinical outcomes associated with the use of oocyte cryopreservation as an investigational option for women who wish to preserve their fertility, to assess egg quality and determine how patient demographics and various chemotherapeutics may affect it.

Hypothesis: Oocyte cryopreservation, which is currently investigational and requires IRB oversight, may be an effective and safe method of fertility preservation for women who may be facing the loss of future fertility due to medical or non medical reasons, with resulting future successful pregnancies. The process of fertility preservation will have a perceived improvement on patient quality of life. Egg quality will be impacted by patient age and alkylating chemotherapy but not other agents or demographic characteristics.

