We will obtain a structured fertility focused quality of life questionnaire (FertiQol) and survey to assess one year after harvest the impact of the process. We will compare cancer patients to those patients undergoing oocyte cryopreservation for non-medical reasons. FertiQol is scored based on the standards of the assessment tool in a quantitative manner. The structured interview will be assessed in a qualitative manner.

Duration: Until the completion of our investigational study and the patient outcome follow-up one year following oocyte harvest.

Location: Female patients will be identified and consented and all study procedures will be conducted through the Division of Reproductive Endocrinology and Infertility, Department of Obstetrics and Gynecology, University of Illinois at Chicago (UIC).

Participant Selection and Enrollment

This study will enroll up to 50 women of reproductive age over 5 years at UIC, in three different categories:

1. Women of reproductive age who are diagnosed with cancer or any disease whose treatment or its progression may impair their reproductive potential.
2. Women undergoing standard In Vitro Fertilization to treat infertility who experience unforeseen events that halt the treatment cycle, such as adverse reactions to hormonal hyperstimulation, inappropriate endometrial receptivity, inability of the partner to provide a semen sample on the day of the egg retrieval or who are unable to consent to freezing of embryos so that the eggs can be cryopreserved and not discarded, as is standard procedure currently.(e.g., failed testicular sperm aspirations, inability to collect or unexpected need to be out of town or patients with ethical objections to freezing of embryos).

3. Women seeking oocyte cryopreservation for non medical reasons such as deferred childbearing.

Women seeking fertility preservation are referred for a comprehensive consultation with a Reproductive Endocrinologist to discuss the range of treatment options available to her. Only patients who choose oocyte cryopreservation as their method of fertility preservation will be enrolled in the study.

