Standard Oocyte Storage: All cryopreserved oocytes will be transferred to Reprotech, Ltd. (RTL) in St. Paul, MN for storage and subsequent release. Reprotech, Ltd. is an FDA-compliant and American Association of Tissue Banks (AATB)-accredited long term storage facility for reproductive tissues. Patients will execute a separate storage agreement with Reprotech, Ltd which defines the length of storage, shipping requirements, infectious

disease screening and testing and disposition of the tissues in the event of the patient's death.

Standard Infectious Disease Screening and Testing: Banking and subsequent use of oocytes is regulated by the Food and Drug Administration (FDA). In order to be prepared for any future requirement, patients will be tested and screened for a number of infectious diseases prior to banking their oocytes. The screening and testing that will be performed are the same as would be performed on an anonymous reproductive tissue donor and include a physical examination and a standard questionnaire for reproductive tissue donors. The testing that will be performed is mandated for donors of reproductive tissues and must be performed within 30 days of oocyte retrieval. The testing will be performed by LifeSource Blood Services, IL and Viromed Laboratories, MN. This way, the tissue could potentially be used by the patient herself, but it could also be suitable for future use in another individual (such as a gestational surrogate) if indicated by the patient's medical condition (e.g., IVF with embryo transfer to a gestational carrier for a patient without a uterus). In addition, a sample of the patient's blood (plasma) will be stored with the oocytes at Reprotech Ltd., St. Paul, MN, to permit any future testing requirements under federal tissue banking regulations. In spite of storing blood plasma, it is still possible that federal regulations may change and therefore, it may not be possible to perform the appropriate testing to permit heterologous use of the tissue in the future..

Establishment and Maintenance of the Outcome Data: Subjects in the study will agree to maintain contact with the investigators, as outlined in the consent form.

Quality of Life Assessment

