Specifically, they will agree to notify the investigators of any changes in their contact information. Study participants will be contacted on an annual basis using the "Investigational Oocyte Cryopreservation Follow-up Call Script" to determine any subsequent attempts to utilize the stored oocytes for the purpose of initiating a pregnancy, along with the outcome of the attempt. An additional follow up email script will also be added to this research. In addition, patients will complete the Ferti-Qol questionnaire at the one year time point. All other dispositions of the oocytes will also be recorded. Individual files will be kept active until all oocytes have been utilized, disposed of in some other way, or ten years following storage, whichever comes first. Patients will be assigned a research number and data will be de-identified. All de-identified data and the master code list will be stored in a locked file cabinet in a locked office and in a password-protected computer in a locked office by the PI and only the co-investigators and the PI will have access to the data.

The subject's participation in this study may involve the following risks;

Standard Ovarian Stimulation: The ovarian stimulation step often causes a sense of fullness or bloating, which usually goes away within a few days after the retrieval. In about 1% cases, patients will develop ovarian hyperstimulation syndrome (OHSS) a serious complication resulting in the accumulation of fluid in the abdominal cavity. This

complication is self-limited, but severe cases may require several days of hospitalization for fluid management. In patients facing a cancer diagnosis, the use of fertility medication will cause a significant increase in two ovarian hormones, estrogen and progesterone, which could potentially worsen the prognosis for the cancer. However, in the case of most cancers the use of fertility drugs does not appear to worsen the chances for cure. Nevertheless, patients will need to discuss with their medical oncologist the pro's and con's of fertility drug use prior to undertaking oocyte cryopreservation.

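### Does the protocol's Duration line end all follow-up at one year, against annual contact and files kept open for up to ten years?

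*Protocol*

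**What the plan says.** Four parts of the protocol bear on how long women are followed.

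- **Study Design, Duration line:** "Until the completion of our investigational study and the patient outcome follow-up one year following oocyte harvest". The paragraph just above it places the FertiQoL questionnaire and the survey one year after harvest.
- **Study Design, Research Design & Methodology:** women with stored oocytes are contacted every year about any warming procedure and its result. No end date is given.
- **Study Procedures, outcome data and Quality of Life Assessment:** "Study participants will be contacted on an annual basis", and the purpose is "to determine any subsequent attempts to utilize the stored oocytes for the purpose of initiating a pregnancy, along with the outcome of the attempt". The same paragraph says that "patients will complete the Ferti-Qol questionnaire at the one year time point", and that individual files are "kept active until all oocytes have been utilized, disposed of in some other way, or ten years following storage, whichever comes first". For the contact obligation itself the protocol points elsewhere: "Subjects in the study will agree to maintain contact with the investigators, as outlined in the consent form".
- **Purpose & Objective:** "To determine the long term benefits, in particular impact on patient quality of life and clinical outcomes associated with the use of oocyte cryopreservation". The Conclusion and the Anticipated Results sections add oocyte survival, pregnancy, live birth and birth defects.

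Enrolment is described as follows: "This study will enroll up to 50 women of reproductive age over 5 years at UIC".

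**The concern.** The Duration line is the one place that sets out to say how long the study lasts, and its only date is one year after harvest. It attaches that date to patient outcomes in general and does not name quality of life. Elsewhere the protocol often uses the word outcome for reproductive results. Completion is not tied to a date or an event; the only stopping rule, in Data Safety & Monitoring, concerns an unfavourable balance of risk and benefit, which is early termination and not a planned end.

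Someone reading that line alone could close follow-up at one year. Many of these women are awaiting cancer treatment or deferring childbearing, so use of the oocytes within a year is not what one would expect. The long-term clinical part of the objective would then be largely unobserved. The one-year quality-of-life comparison would be unaffected, as would egg quality, which is scored before freezing.

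**Working it through.** The protocol states no figure to reproduce here, since no sample size, power or error rate is involved. The check is timeline arithmetic under each possible reading, followed by a comparison of the readings with the text.

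**Inputs.** Up to 50 women over 5 years (Participant Selection and Enrollment); one year after harvest (Duration line); ten years after storage (Study Procedures, outcome data).

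**Assumptions.** Full and even enrolment, harvest and storage soon after enrolment, no deaths or losses to follow-up, and contact continuing while a file is active.

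| Reading | Follow-up per woman | Woman-years | Shortfall from 500 |
|---|---|---|---|
| A. Each woman stops at one year | 1 | 50 × 1 = 50 | 450 (450/500 = 90%) |
| B. Study closes when the last woman reaches one year, at year 5 + 1 = 6 | 1 to 6, mean (1 + 6)/2 = 3.5 | 50 × 3.5 = 175 | 325 (325/500 = 65%) |
| C. One year is the quality-of-life point; contact runs while the file is active, at latest to year 5 + 10 = 15 | up to 10 | up to 50 × 10 = 500 | 0 |

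The 500 is a ceiling, because a file closes early once all oocytes are used or otherwise disposed of. The shortfalls under A and B are therefore upper bounds.

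**Which reading fits the text?**

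1. *Wording of the line.* It joins two conditions, completion of the study and the one-year follow-up. A period that runs until both are met is not capped by the second alone. Reading A drops the first condition.
2. *Position of the line.* It comes straight after the paragraph that puts FertiQoL and the survey at one year, and Study Procedures puts FertiQoL at the same point. That assessment is the natural meaning of the one-year follow-up.
3. *Annual contact.* It appears both in the design section and in the procedures. Under A it would shrink to a single contact.
4. *Ten-year limit.* Under A no woman is followed beyond year 1, and under B none beyond year 6. The limit would never be reached under either; it has work to do only under C.
5. *Stated expectations.* The Rationale insists on prospective follow-up despite the long time frame. The Conclusion expects pregnancy and live-birth data by the end of the study. Both presuppose more than one year.

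All five points favour C over A. Points 2, 4 and 5 also favour C over B. No procedure tells staff to stop contact at one year.

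**The case for a change.** The strongest case for a change is that study duration is fixed by the protocol, not by the SAP, and that this line leaves it open. Completion is undefined on every reading. Because of that, the joint wording alone does not exclude reading B: a sponsor could declare the study complete when the last woman reaches one year and satisfy the sentence literally. The rule on keeping files active is also not expressly a rule that contact continues; the protocol never gives annual contact an end date. An edit using end points already in the protocol would cost little.

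Part of this stands. Completion is undefined, and the link between an active file and continued contact is inferred. The inference is a short one, however. The file rule sits in the same paragraph as the annual contact, and a file cannot be closed on use or disposal unless someone finds out that this has happened. The length of contact may also be settled in the consent form, to which the protocol refers and which is not shown, so it cannot be called missing.

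What does not stand is the size of the harm. The 90% and 65% shortfalls need a reading that the rest of the protocol does not favour, and they also equate an active file with ten years of follow-up.

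**Conclusion.** No change to the plan follows. The Duration line is a loose summary, and the specific procedures supply what it leaves out: a quality-of-life assessment at one year, annual contact about oocyte use, and files open for up to ten years. On the reading that these passages support, the loss of follow-up is zero. The losses of up to 450 or 325 woman-years arise only if the line is read as the end of the study.

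This conclusion assumes that staff work from the procedures and do not treat the summary line as a stopping rule, and that annual contact continues while a file is active. Clarifying the line would add no contact beyond those already set out and would alter no endpoint, sample size or analysis. It is a gap in detail that those running the study can fill sensibly from the protocol itself.

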The ASRM and ACOG practice guidelines stating that oocyte cryopreservation is still considered investigational and may only be offered with appropriate informed consent in a research setting with IRB oversight necessitate more rigorous investigation into the methods and consequences of oocyte cryopreservation in order for it to evolve from an experimental to a standard procedure,. To this end, this protocol has been designed to identify suitable candidates for oocyte cryopreservation and to systematically follow them in order to assess the long term benefits and outcomes associated with its use. During our investigation we will explore egg quality and quality of life measures.

Lastly, the implementation of fertility preservation counseling and obtaining of oocytes for future use is believed to have a positive impact on a cancer patient's quality of life. We will obtain a structured fertility focused quality of life questionnaire and survey to assess one year after harvest the impact of the process. We will compare cancer patients to those patients undergoing oocyte cryopreservation for non-medical reasons.

Study Design

Research Design & Methodology: We will conduct a prospective study to assess the long term benefits and outcomes of the existing oocyte cryopreservation methods for fertility preservation in women with a potential medical or non medical risk of loss of fertility. Women wishing to preserve their oocytes using cryopreservation will be informed of the risk and limitations of the procedures involved in ovarian hyperstimulation, oocyte recovery, cryopreservation and subsequent viability after warming. Women who consent to the procedure will undergo standard controlled ovarian hyperstimulation (COH) and oocyte retrieval procedures currently in use for IVF. Following harvest all eggs obtained will be evaluated for degree of fragmentation and maturation status. The oocytes will be cryopreserved using kits of media and devices currently approved for use in the vitrification of fertilized eggs and embryos, and the cryopreserved oocytes will be stored for future patient use in a long term storage facility in Minnesota (Reprotech Ltd.). Patients with stored oocytes will be contacted annually to determine the outcome of any oocyte warming procedures (oocyte thawing, fertilization and embryo transfer).

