Informed Consent Procedure: Participation in this study is entirely voluntary. Choosing to not participate will not impact the care received at this institution. Following selection and counseling as outlined above, all subjects will be required to provide informed consent for participation in the study. All potential subjects will be informed of the risks of the procedure. Information about oocyte retrieval and cryopreservation will be provided and the experimental nature of oocyte cryopreservation will be emphasized. They will be informed of the extent to which they may benefit from the study. The subject will be granted time to read the informed consent document, and all questions will be answered to her satisfaction.

Inclusion Criteria:

- Women aged ≥ 18 and ≤ 40 years.
- Women able to defer definitive cancer therapy for 21 to 30 days.
- Women diagnosed with cancer or any disease whose treatment or its progression may impair their reproductive potential (this would include but not be limited to cancer patients requiring treatment with chemotherapy or radiation, patients with rheumatologic diseases such as lupus, rheumatoid arthritis and ulcerative colitis and patients with genetic predisposition to cancers).
- Women undergoing standard In Vitro Fertilization to treat infertility who experience unforeseen events that halts the treatment cycle.
- Women seeking oocyte cryopreservation for non medical reasons, such as deferred childbearing.
- Women who are carriers of BRCA mutations predisposing them to cancer.
- Otherwise healthy females.
- Ability and willingness to comply with study protocol
- Informed written consent, prior to any study-related procedure not part of normal care, with the understanding that the subject may withdraw consent at any time without prejudice to their future medical care

Exclusion Criteria:

- Current pregnancy
- Serum FSH ≥ 10 mIU/ml for patients having egg freezing for a medical indication
- Serum FSH ≥ 10 mIU/ml for patients having egg freezing for social reasons
- Women who upon undergoing psychological assessment are found to be unable to provide informed consent or are expected to be unable to cope with the rigor of the study)
- Patients with extensive disease whose therapy is deemed palliative by the medical oncologist.

Compensation to Subjects for Participation:

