Subjects will not receive compensation for participation in the study. No direct reimbursement will be made to the subjects or to their families. All costs will be billed to the subject or subject's insurance. All non-covered services are the subject's responsibility.

In the event of injury or illness resulting from the research procedures, medical treatment for injuries or illness is available through the University of Illinois at Chicago Medical Center. Payment for this treatment will be the subject's responsibility.

Study Procedures

Following selection, potential subjects must be informed fully about the process involved and clinical outcomes that can be reasonably expected. Counseling by a qualified mental health professional will also be required. After obtaining informed consent, enrolled subjects will participate in the following:

Standard Oocyte Harvesting Procedure: Subjects will undergo controlled ovarian hyperstimulation according to established clinical protocols utilized in the In Vitro Fertilization Program at UIC. Briefly, they will be treated with variable dosages of injectable gonadotrophins over a period of 8 to 12 days. Response will be monitored using vaginal ultrasound and serum estradiol levels. When appropriate follicle maturation has been achieved, a single dose of human chorionic gonadotropin (hCG) will be administered to induce final oocyte maturation. Thirty-six hours after hCG administration, the subject will undergo standard transvaginal oocyte retrieval under ultrasound guidance. The procedure takes approximately 20 minutes and is carried out under conscious sedation with Fentanyl and Versed. The oocytes are immediately handed off to the embryology technicians in the IVF laboratory.

Investigational Oocyte Cryopreservation: Oocyte cryopreservation will be carried out using the technique of vitrification, which has resulted in high oocyte survival, fertilization, pregnancy and implantation rates in case series reported in the literature (Oktay et al, 2006; Fadini et al, 2009; Cao et al, 2009, Smith et al, 2010). Oocytes will be cryopreserved using modifications of vitrification techniques described by Cao et al, 2009, Griffio and Noyes, 2009, Nagy et al, 2009 and Smith et al, 2010. **Prior to cryopreservation, when eggs are being evaluated by the embryologist; fragmentation score and maturation status will be formally evaluated and recorded.**

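### The protocol does not specify that the embryologist grading egg quality is masked to chemotherapy history or age, the two factors it predicts will matter, so expectation bias in the fragmentation score is possible.

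*Protocol*

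**What the plan says.** The Study Design section says that "Following harvest all eggs obtained will be evaluated for degree of fragmentation and maturation status". Study Procedures, under Investigational Oocyte Cryopreservation, adds who grades and when: before cryopreservation, "when eggs are being evaluated by the embryologist; fragmentation score and maturation status will be formally evaluated and recorded". The preceding paragraph on harvesting says that "The oocytes are immediately handed off to the embryology technicians in the IVF laboratory", and the Location paragraph says that "all study procedures will be conducted through the Division of Reproductive Endocrinology and Infertility". The grade is thus given locally, during the embryologist's evaluation of the eggs.

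The Hypothesis paragraph under Purpose & Objective states the expected pattern: "Egg quality will be impacted by patient age and alkylating chemotherapy but not other agents or demographic characteristics".

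The nearest thing to a safeguard is under Quality of Life Assessment: "Patients will be assigned a research number and data will be de-identified". It stands with the provisions on locked storage and restricted access, and is not tied to the moment of grading. The protocol nowhere mentions masking of the grader, a second or outside reader, stored images, or a named fragmentation scale with criteria.

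**The concern.** A fragmentation score with no named scale leaves room for judgement. A grader who knows that a woman is older, or has received an alkylating agent, may resolve borderline eggs in line with the hypothesis. One who knows that she received a different agent may do the same in the other direction, because the hypothesis also predicts where no effect will be seen. Either shift would be read as support for the hypothesis.

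What the grader knows at the time of scoring is a matter of laboratory procedure. It belongs in the protocol, and an analysis plan cannot restore masking afterwards. The eggs are then vitrified and sent to an outside storage facility, and no images are planned, so as written there is no route to a later masked re-reading of the pre-freeze grade.

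At stake is the egg-quality objective. Quality of life, pregnancy and birth outcomes are not touched. Maturation status is graded at the same time, but the argument about judgement applies mainly to fragmentation.

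**Working it through.** **What the text supports.** Set side by side, the passages establish three things: a local embryologist grades during the evaluation before freezing; the factors expected to matter are stated in advance; and no passage separates the grader from information on those factors. They do not establish that the grader actually has that information.

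**Size.** The protocol gives no score distribution, reader agreement, effect size or group sizes by age or chemotherapy exposure, so there is no figure to reproduce. The only document input is the ceiling on enrolment: "This study will enroll up to 50 women of reproductive age over 5 years at UIC, in three different categories". Everything else below is an assumption, including the good/poor split, for which the protocol sets no cut-off.

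Assumptions: 25 v 25 women; m = 10 eggs each (range 8 to 12); 80% graded good; within-woman correlation ρ = 0.1 (range 0.05 to 0.20); drift of 10 points in one group, that is, one egg in ten graded down with no true difference.

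Formulas: design effect DE = 1 + (m − 1)ρ; SE = sqrt(DE × [p1(1 − p1)/(n1·m) + p2(1 − p2)/(n2·m)]).

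- Base case: DE = 1 + 9 × 0.1 = 1.9; SE = sqrt(2 × 0.16 × 1.9/250) = 0.0493. Ten points is 0.10/0.0493 = 2.0 SE.
- 12 eggs, ρ = 0.05: DE = 1.55; SE = sqrt(2 × 0.16 × 1.55/300) = 0.0407; 2.5 SE.
- 8 eggs, ρ = 0.20: DE = 2.4; SE = sqrt(2 × 0.16 × 2.4/200) = 0.0620; 1.6 SE.
- Base case with the downgraded group's variance taken at 70%, as the scenario implies: SE = sqrt((0.16 + 0.21) × 1.9/250) = 0.0530; 1.89 SE; two-sided p about 0.06.
- 5 exposed v 45 unexposed women, closer to what may apply to chemotherapy: SE = sqrt(0.16 × 1.9 × (1/50 + 1/450)) = 0.0822; 1.2 SE. With 70% in the exposed group, SE = sqrt(1.9 × (0.21/50 + 0.16/450)) = 0.0930; 1.1 SE.

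**What this means for a test.** With no true difference, the chance of crossing 1.96 in the drifted direction is the normal probability above (1.96 − drift/SE), against 2.5% without drift. It is about 53% in the base case, 47% with the 70% variance, 36% to 69% across the 25 v 25 range, and 23% for 5 v 45 (19% with the 70% variance). A drift of 5 points in the base case (1.0 SE) gives about 17%.

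**The case against.** **Silence is not evidence of unmasked grading.** The protocol does not say what the embryologist knows. This stands: the supportable statement is that no masking is specified. A reader might infer that the grader knows each woman's history and that the scores will be biased; the document shows neither.

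**The hypothesis names no direction and no indication.** It says that age and alkylating chemotherapy will affect egg quality. That the eggs of older or exposed women should be worse is a reasonable inference, but it is the reader's. A reader might also infer that the reason for freezing must be masked because cancer patients are compared with non-medical patients; that comparison is planned for quality of life. Both points stand, so the factors of concern are chemotherapy history and age.

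**Few women may be exposed to chemotherapy when the eggs are graded.** The inclusion criteria require "Women able to defer definitive cancer therapy for 21 to 30 days", so harvest generally precedes definitive cancer therapy. This stands and narrows the chemotherapy side. It does not remove it: the risk paragraph on oocyte retrieval allows for a delay to additional chemotherapy, which hints at earlier treatment, and the rationale includes autoimmune disorders that may require gonadotoxic agents. Age varies across all participants, from 18 to 40.

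**Drift of this size need not produce a significant result.** This stands. A reader who takes the base case alone might conclude that re-grading one egg in ten would create a significant effect. Using the 70% variance, or an unequal split, takes the shift below 1.96 SE.

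**Masking would be partial.** Age may appear on identity labels. The laboratory is likely to know of halted IVF cycles, for example when no sperm sample is available on the day of retrieval. This limits the gain but does not cancel it, because chemotherapy history can be kept off the grading sheet.

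**Coded images could allow later masked reading.** True in principle, but the protocol plans none.

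**Conclusion.** The concern holds in limited form. The protocol places the research grade within the local embryologist's evaluation of the eggs, states in advance which factors should matter, and specifies no masking to those factors and no fragmentation scale. Expectation bias in the fragmentation score is possible; the document does not show that it occurs, and its size cannot be derived from it.

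On the stated assumptions, a 10-point drift is about 1.2 to 2.5 standard errors with both groups' variance at 80%, and 1.1 to 1.9 in the two cases shown with 70% in the downgraded group. That is enough to contribute to an apparent effect and raise the false-positive rate well above nominal, but not enough to create one reliably. The range rests on assumed egg counts, proportions, correlation and group splits; only the ceiling of 50 women comes from the protocol. Because the remedy is cheap and the grade cannot be repeated as the study is written, the change is worth making, though it bears on only one of several objectives.

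**What to change.** Amend the Investigational Oocyte Cryopreservation paragraph of Study Procedures as follows.

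- Name one fragmentation scale, with its grading criteria.
- Have the same embryologist record fragmentation and maturation on a sheet that carries only the research number.
- Keep chemotherapy history, and age where identity checks allow, off the grading paperwork, and link them only after the grades are entered.
- Record each case in which the grader knew the history, and run a sensitivity analysis without those cases.
- State as a limitation that masking of age and of halted-IVF cases will be incomplete.

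The cost is a grading sheet and a minor change to laboratory paperwork. No extra reader is needed and patient care does not change. The downside is that masking will be only partial, so the sensitivity analysis and the stated limitation must go with it.
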